#### 16.4.1 ECG MARKEDLY ABNORMAL CRITERIA

For all patients in the safety analysis population, the maximum QTcF interval will be summarized using frequency tables for each SHR0302 dose level, placebo and overall in treatment phase for values of clinical importance using the range criteria below.

- Absolute values for post baseline QTcF interval will be classified as:

Cumulative Category:

- ≤ 450 msec
- > 450 msec
- > 480 msec
- > 500 msec

Interval Category:

- ≤ 450 msec
- > 450 to ≤ 480 msec
- > 480 to ≤ 500 msec
- > 500 msec

- Change from Baseline for QTcF interval will be classified as:

Cumulative Category:

- <0 msec increase from baseline
- ≥ 0 msec increase from baseline
- >30 msec increase from baseline
- >60 msec increase from baseline

Interval Category:

- <0 msec increase from baseline
- ≥ 0 to ≤ 30 msec increase from baseline
- > 30 to ≤ 60 msec increase from baseline
- >60 msec increase from baseline

The maximum QTcF interval will also be summarized similarly for 8 mg QD total, 4 mg BD total, 4 mg QD total, Placebo only and overall during the whole study period.

## 16.5 VITAL SIGNS

The following Vital Signs measurements will be reported for this study:

- Systolic Blood Pressure (mmHg)
- Diastolic Blood Pressure (mmHg)
- Heart Rate (beats/min)
- Temperature (°C)
- Weight
- Height

The following summaries will be provided for vital signs data:

- Actual and change from baseline by visit
- Incidence of abnormal values according to markedly abnormal criteria
- Listing of patients with vital signs measurements

### 16.5.1 Vital Signs Markedly Abnormal Criteria

Markedly abnormal quantitative Vital Signs measurements will be identified in accordance with the following predefined markedly abnormal criteria detailed in below table:

Document: \\ieedc-vnasc01\Biosdata\Reistone\SHR0302\CZA55021\Biostatistics  
Author: [REDACTED]

Version Number:  
Version Date:

Final v1.2  
23Mar2021

Template No: CS\_TP\_BS016 Revision 5  
Effective Date: 01Apr2018

Reference: CS\_WI\_BS005

Variable	Unit	Low	High
SBP	mmHg	≤ 90 mmHg AND change from baseline ≤ -20 mmHg	≥ 180 mmHg AND change from baseline ≥ 20 mmHg
DBP	mmHg	≤ 50 mmHg AND change from baseline ≤ -15 mmHg	≥ 105 mmHg AND change from baseline ≥ 15 mmHg
Heart Rate	Bpm	≤ 50 bpm AND change from baseline ≤ -15 bpm	≥ 120 bpm AND change from baseline ≥ 15 bpm
Body temperature	°C	NA	≥ 38.3 °C AND change from baseline ≥ 1.1 °C
Weight	Kg	percentage change from baseline ≤ -7.0 %	percentage change from baseline ≥ 7.0 %

## 16.6 PHYSICAL EXAMINATION

Physical examination data will be listed only.

## 16.7 OTHER SAFETY ASSESSMENTS

Female patients of childbearing potential will be tested for serum beta-human chorionic gonadotropin ( $\beta$ -hCG) at screening visit. In addition, urine  $\beta$ -hCG test will be done at baseline and at each study visit until the end of follow-up period. If at any point there is a case of a positive urine  $\beta$ -hCG test, and this is confirmed by serum  $\beta$ -hCG, the patient will be withdrawn from the study and all the necessary follow up will be conducted. Urine pregnancy test will be done in females of childbearing potential only. Pregnancy tests data will be listed.

Phase II liver chemistry stopping and follow up criteria have been designed to assure patient safety and evaluate liver event etiology (in alignment with the FDA premarketing clinical liver safety guidance). Please refer to section 7.3.9 of the protocol for details. Liver Event Follow up Assessments and Liver Event Alcohol intake will be listed.

Supplemental lab data will be listed

Microscopy data, if available, will be listed.

A listing will be provided for patients whose trial participation are impacted by COVID-19, including patient number and site number together with a description of the impact. These protocol deviations are documented in [REDACTED] management system.

## APPENDIX 1. PROGRAMMING CONVENTIONS FOR OUTPUTS

### Output Conventions

Outputs will be presented according to the [REDACTED] guidelines and template for outputs conventions.

#### Dates & Times

Depending on data available, dates and times will take the form DDMMYY YYYY hh:mm:ss.

#### Significant Digits of Summary Statistics

1 Summary statistics are displayed with the following digits.

Description	Characteristic	Number of decimal places
Count	n	0
Count corresponding to the number of patients for a treatment group	N	0
Mean	Mean	As in source + 1
Standard Deviation	SD	As in source + 1
Confidence Interval	CI	As in source + 1
Minimum	Min	As in source
Median	Median	As in source + 1
Maximum	Max	As in source
Percentage	%	1 *
P-value	P-value	3 decimal places. If the value is less than 0.001, then it will be shown as "<0.001". If P-value cannot be calculated, "-" is shown. If test is not performed, nothing is shown.

\* Number of decimal places can be two, if necessary.

2 If the source has more than 5 significant digits, the above would be replaced with the corresponding number of significant digits.

#### Spelling Format

English US.

Document: \\ieedc-vnasc01\Biosdata\Reistone\SHR0302\CZA55021\Biostatistics

Author: [REDACTED]

Version Number:

Final v1.2

Version Date:

23Mar2021

Template No: CS\_TP\_BS016 Revision 5  
Effective Date: 01Apr2018

Reference: CS\_WI\_BS005

### Presentation of Treatment Groups

For outputs, treatment groups will be represented as follows and in that order:

Treatment Group	For Tables, Listings and Graphs
SHR0302 8mg QD during the whole study period	8mg QD
SHR0302 4mg BD during the whole study period	4mg BD
SHR0302 4mg QD during the whole study period	4mg QD
Initially randomized to Placebo	Placebo
Placebo during the treatment phase and SHR0302 8mg QD after treatment phase	Placebo->8mg QD
Placebo during the treatment phase and SHR0302 4mg BD after treatment phase	Placebo->4mg BD
Placebo during the treatment phase and SHR0302 4mg QD after treatment phase	Placebo->4mg QD
Screen failure	Screen failure

For some tables related to TEAE and ECG markedly abnormal criteria, treatment group will be presented as follows.

Treatment Group	For TEAE and ECG Markedly Abnormal Criteria Tables
SHR0302 8mg QD during the whole study period+ Placebo->8mg QD group after treatment phase	8mg QD total
SHR0302 4mg BD during the whole study period + Placebo->4mg BD group after treatment phase	4mg BD total
SHR0302 4mg QD during the whole study period + Placebo->4mg BD group after treatment phase	4mg QD total

Treatment Group	For Tables, Listings and Graphs
Placebo group during treatment phase	Placebo only

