9.3.4.4 Safety Analysis

Summaries of safety data will be based on the safety analysis set.

Adverse events will be grouped by Medical Dictionary for Regulatory Activities (MedDRA) system organ class (SOC) and preferred term (PT) and summarized by actual treatment.

Treatment emergent AEs are defined as AEs which commence on or after the time of start of IP administration. Adverse events without an onset date or time or AEs with an onset date of the date of IP administration but without an onset time will be defined as treatment emergent, except if an incomplete date (e.g., month and year) clearly indicates that the event started before administration of IP or if the AE stop date indicates that the event stopped before administration of IP.

Treatment emergent AEs will be summarized for each SHR0302 dose level and placebo. The number and percentage of subjects experiencing AEs and the number of TEAEs will be tabulated.

The following summaries will be presented:

- ✓ Overall summary of TEAEs.
- ✓ All TEAEs by SOC and PT.
- ✓ All TEAEs by SOC, PT, and severity.
- ✓ All TEAEs by SOC, PT, and relationship to IP.
- ✓ Serious AEs by SOC and PT.

Separate listings will be prepared for deaths and AEs leading to study discontinuation.

Observed values and actual changes from baseline of continuous laboratory parameters (hematology and biochemistry), dipstick urinalysis results evaluation (Normal, Abnormal Not Clinically Significant, or Abnormal Clinically Significant), vital signs, and ECG parameters will be summarized at each protocol scheduled time point, by actual treatment at each time point. Actual values and actual changes from baseline will be presented. Categorical outcomes will be summarized by frequency tabulations. Abnormal laboratory values will be flagged and will be identified in the listings. Microscopy data, if available, will be listed.

Shift tables representing categorical change of laboratory results from baseline to each post baseline visit will be presented. QTcF prolongation and ECG interpretations will be summarized by frequency tabulations.

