### 16.3 LABORATORY EVALUATIONS

Results from the central laboratory will be included in the reporting of this study for Hematology, Chemistry, Urinalysis and Others. All laboratory assessments will be listed in the outputs.

Presentations will use SI Units. All laboratory data will be summarized and listed for all patients in the SS set by visits where data are collected.

Quantitative laboratory measurements reported as “< X”, i.e. below the lower limit of quantification (BLQ), or “> X”, i.e. above the upper limit of quantification (ULQ), will be converted to X for the purpose of quantitative summaries, but will be presented as recorded, i.e. as “< X” or “> X” in the listings.

Quantitative laboratory measurements will be compared with the relevant laboratory reference ranges in SI units and categorized as:

- Low: Below the lower limit of the laboratory reference range.
- Normal: Within the laboratory reference range (upper and lower limit included).
- High: Above the upper limit of the laboratory reference range.

The following summaries will be provided for laboratory data:

- Actual and change from baseline by visit (for quantitative measurements)
- Incidence of abnormal values according to normal range criteria
- Shift tables representing categorical change of laboratory evaluation results from baseline to each post baseline
- Listing of patients with laboratory results

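### SAP Appendix 1 gives the general Placebo label no Week 8 limit, and SAP 16.3 to 16.5 do not say which label applies once placebo patients switch to SHR0302

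*SAP*

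**What the plan says.** Protocol 9.3.4.4 states that laboratory parameters, urinalysis, vital signs and ECG parameters are to be "summarized at each protocol scheduled time point, by actual treatment at each time point". Under Protocol 1.3 and 4.2, every placebo patient who enters the 8-week extension receives one of three SHR0302 regimens, pre-assigned 1:1:1. Entry is optional.

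SAP Appendix 1, under Presentation of Treatment Groups, lists the labels for tables, listings and graphs. The *Placebo* label is "Initially randomized to Placebo". Three further labels cover the switch sequences; the first is defined as "Placebo during the treatment phase and SHR0302 8mg QD after treatment phase". A second list contains *Placebo only*, defined as "Placebo group during treatment phase", together with a total label for each dose. Its scope is restricted: "For some tables related to TEAE and ECG markedly abnormal criteria, treatment group will be presented as follows".

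SAP 16.3 says: "All laboratory data will be summarized and listed for all patients in the SS set by visits where data are collected". It then asks for by-visit values, incidence of abnormal values, and shift tables. SAP 16.4 asks for the same three kinds of ECG summary. SAP 16.5 asks for "Actual and change from baseline by visit" and for incidence of markedly abnormal vital signs. Apart from the maximum-QTcF tables in 16.4.1, none of these states a study phase or a set of treatment columns.

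**The concern.** Placebo is the only concurrent control for the laboratory, ECG and vital-sign data, and that control ends at Week 8. After that, a placebo-randomised patient in the extension contributes information about SHR0302. A label that follows randomisation without a time limit would put those on-drug values in the control column.

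In a by-visit or shift table the effect is confined to the rows after Week 8, and Weeks 1 to 8 are untouched. In an incidence table with no phase limit the problem is less visible. If abnormalities are counted over all post-baseline visits, the extra weeks can only raise the placebo count or leave it unchanged, and the table would not show that part of the count arose on drug. SAP 3.1 says the data should help select one or two doses for further development, so a diluted control comparison for safety laboratory values matters.

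**Working it through.** **1. Are the labels mutually exclusive after Week 8?**

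| Label (SAP Appendix 1) | Period stated | Where it applies |
|---|---|---|
| 8mg QD, 4mg BD, 4mg QD | whole study | outputs generally |
| Placebo | none | outputs generally |
| Placebo->8mg QD, ->4mg BD, ->4mg QD | placebo in the treatment phase, active afterwards | outputs generally |
| Placebo only | treatment phase | some TEAE and ECG markedly abnormal tables |

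*Placebo* is the only treatment row with no period. A patient who switches meets both the *Placebo* definition and one *Placebo->dose* definition at Weeks 9, 12 and 16. The labels overlap, and the list gives no rule for choosing between them.

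**2. Which safety tables say what to use?**

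| Output | Phase or columns stated? |
|---|---|
| TEAEs (16.1.1 to 16.1.5) | Yes: treatment phase, then dose totals with Placebo only |
| Maximum QTcF (16.4.1) | Yes: same structure |
| Laboratory by visit, abnormal incidence, shift (16.3) | No |
| ECG by visit, abnormal incidence, shift (16.4) | No |
| Vital signs by visit, markedly abnormal incidence (16.5) | No |

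The contrast between 16.4.1 and 16.5.1 is telling. Both apply markedly abnormal criteria, but only the QTcF section separates the phases.

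**3. Are there data after Week 8 in these tables?** Yes. The Time and Event Table (Protocol 5.12) schedules haematology, chemistry and vital signs at Weeks 9, 12, 16 and 18, and ECG at Weeks 9, 16 and 18.

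**4. Is a departure from the protocol declared?** No. SAP 3.3 lists two changes, the added analysis sets and the per-protocol definition. Neither concerns treatment grouping in safety summaries.

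**5. How many patients could be involved?**

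- Plan's figure: 152 randomised, from 35 evaluable in each of 4 arms with 8% dropout. Check: 35 × 4 = 140. Then 140 × 1.08 = 151.2, rounded up to 152. Dividing instead, 140 / 0.92 = 152.2, which rounds up to 153. The stated 152 is reproduced.
- Placebo arm at 1:1:1:1: 152 / 4 = 38.
- Per switch sequence at 1:1:1: 38 / 3 = 12.7.
- If 8% drop out before Week 8 and every completer enters the extension: 38 × 0.92 = 34.96, about 35 in all, or about 11.7 per sequence.
- The entry rate is not given, so the possible range is 0 to 38.

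**The case against.** The strongest reply is that Appendix 1 is a menu of labels and does not fix the columns of every table. It includes *Screen failure*, which cannot be a column in a post-dose laboratory table on the safety set. It also supplies the *Placebo->dose* labels that a Week 9 to 16 table needs. SAP section 8 leaves format and content to templates, which are not in the public text. SAP 3.3 declares no departure, so the protocol's rule can be taken still to apply. The tables are descriptive, with no between-group testing (SAP section 16), and the main safety outputs already separate the phases.

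Most of this stands. A reader might infer that the tables will print switched patients as placebo, or print them twice. The documents do not show that, because the templates decide it and cannot be seen. A reader might also infer that the follow-up row pools never-exposed placebo patients with patients just off SHR0302. That is not established either: *Follow Up* appears in the list of CRF visits, and Appendix 1 says tables display analysis visits. Nor do the documents give event rates from which the size of any distortion could be calculated.

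The reply does not remove the stated definition. *Placebo* has no Week 8 limit, the time-limited label is reserved for other tables, and sections 16.3 to 16.5 do not choose. The safety-set clause in SAP 5.5 does not settle it: it reassigns patients whose actual treatment differs from their allocation, and switchers receive the sequence they were allocated.

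**Conclusion.** The point holds as a labelling gap that conflicts with the protocol if the general definition is applied literally. On-SHR0302 data from at most about 35 to 38 placebo-randomised patients could then be counted under *Placebo* in the laboratory, ECG and vital-sign tables. The 35 assumes 8% dropout and full extension entry; 38 is the whole arm; the true number could be much lower. The abnormal-value incidence tables carry the most risk because they have no phase limit. The exposure there depends on whether they count over all post-baseline visits, which the SAP does not say.

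The whole-study TEAE and maximum-QTcF tables are not affected, and neither is the Week 8 primary endpoint. The unseen templates may already handle the matter correctly. It should still be settled in the SAP text, because that is the document checked against Protocol 9.3.4.4.

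**What to change.** Amend Appendix 1 and sections 16.3 to 16.5 of the SAP to state that:

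- *Placebo* covers only assessments up to the Week 8 visit, before the first extension dose.
- Later data from placebo-randomised patients who switch appear only under the *Placebo->dose* columns, or under the dose-total columns where those are used.
- Abnormal-value incidence tables for laboratory, ECG and vital signs use the structure of the TEAE and maximum-QTcF tables: a treatment-phase table, then a whole-study table with dose totals and *Placebo only*.
- If follow-up visit data are tabulated, placebo patients who entered the extension are shown separately from those who did not.

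Before the total columns are reused, their definitions need reconciling. Appendix 1 builds *4mg QD total* from the Placebo->4mg BD group, whereas SAP 16.1.1 uses the Placebo->4mg QD group.

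The cost is SAP wording and a check, with edits where needed, of the table templates. No new data are required; the randomised sequence, extension entry and dosing dates are already collected.

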The efficacy, safety, tolerability, and anti-inflammatory data generated by this proposed phase II study will be essential for evaluating the potential of this promising, novel anti-inflammatory agent as a treatment for moderate to severe active ulcerative colitis so that one or two doses can be selected to progress into further clinical development.

Figure 1: Study Design Diagram

---

Document:

\\\ieedc-vnasc01\Biosdata\Reistone\SHR0302\CZA55021\Biostatistics

Author:

[REDACTED]

Version Number:

[figure not shown]
Final v1.2

Version Date:

23Mar2021

Template No: CS\_TP\_BS016 Revision 5  
Effective Date: 01Apr2018

Reference: CS\_WI\_BS005

The sample size calculation is based on pairwise comparison of clinical response at week 8 among SHR0302 8mg, 4mg BD, 4mg QD dose group and placebo group at the 2-sided 0.1 significance level. 57%, 57%, 50%, 30% clinical response are assumed for 8mg QD, 4mg BD and 4mg QD dose group, placebo group at week 8 respectively. The planned sample size of 35 evaluable patients per treatment group will provide 80% global power to detect at least 1 dose group is different from placebo group by using Hochberg's step-p test. The total sample size is 152 randomized patients with consideration of 8% drop out rate. 152 eligible patients will be randomized to achieve an estimated 140 evaluable patients in the study.

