## 8. OUTPUT PRESENTATIONS

Appendix 1 of the analysis plan shows conventions for presentation of data in outputs.

The templates provided with this SAP describe the presentations for this study and therefore the format and content of the summary tables, figures and listings to be provided by ██████████ Biostatistics.

Continuous variables will be summarized using descriptive statistics, i.e., non-missing observations, mean, median, standard deviation (SD), minimum, and maximum.

Categorical variables will be summarized by counts and percentages. Unless otherwise stated, the calculation of proportions will be based on the population of interest. Counts of missing observations will be included in the denominator, unless specified.

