### **16.1.1 All TEAEs**

An overall summary of TEAEs in treatment phase will be provided. The number and percentage of patients experiencing AEs and the number of TEAEs will be tabulated.

Incidence of TEAEs will be presented by System Organ Class (SOC) and Preferred Term (PT) and summarized in treatment phase for each SHR0302 dose level , placebo and overall.

All TEAEs during the whole study period will also be summarized for the following groups similarly.

- 8 mg QD total: 8mg QD during the whole study period+ Placebo->8mg QD group after treatment phase
- 4 mg BD total: 4 mg BD during the whole study period + Placebo->4mg BD group after treatment phase
- 4 mg QD total: 4 mg QD during the whole study period + Placebo->4mg QD group after treatment phase
- Placebo only: Placebo group during treatment phase

Incidence of TEAEs will also be broken down further as shown in the following sections.

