### **16.1.2 TEAEs of Serious Infection**

A serious infection during the study is defined as any infection (viral, bacterial, and fungal) requiring hospitalization or parenteral antimicrobials. The patient must be discontinued from the study. Serious infection will be identified as those records with a response of "Yes" to the item "Is this a serious infection defined in protocol?" on the "Adverse Events" form of the eCRF. Serious Infection in treatment phase will be summarized by SOC and PT for each SHR0302 dose level , placebo and overall. The number of patients with at least one serious infection will be presented and 95% CI will be calculated using the Clopper-Pearson method. TEAEs of serious infection will also be summarized similarly for 8 mg QD total, 4 mg BD total, 4 mg QD total, Placebo only and overall during the whole study period.

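### SAP Appendix 1 builds the 4mg QD safety total from the wrong placebo switchers, contradicting SAP 16.1.1

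*SAP*

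**What the plan says.** SAP 16.1.1 sets out the pooled groups for whole-study adverse events. For the lowest dose it reads: "4 mg QD total: 4 mg QD during the whole study period + Placebo->4mg QD group after treatment phase". The 8mg QD and 4mg BD pools there follow the same rule: the randomized arm plus the placebo patients who switch to that same regimen.

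SAP Appendix 1, under Presentation of Treatment Groups, gives a second set of definitions for the same columns and states its scope: "For some tables related to TEAE and ECG markedly abnormal criteria, treatment group will be presented as follows". Its 8mg QD and 4mg BD rows match 16.1.1; the latter is "SHR0302 4mg BD during the whole study period + Placebo->4mg BD group after treatment phase". The next row, labelled 4mg QD total, reads: "SHR0302 4mg QD during the whole study period + Placebo->4mg BD group after treatment phase".

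Later sections use the pooled columns by name without redefining them. SAP 16.1.2 says: "TEAEs of serious infection will also be summarized similarly for 8 mg QD total, 4 mg BD total, 4 mg QD total, Placebo only". SAP 16.4.1 says: "The maximum QTcF interval will also be summarized similarly for 8 mg QD total, 4 mg BD total, 4 mg QD total, Placebo only". The sections on relationship, severity, discontinuation, serious events, fatal events and deaths do the same.

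**The concern.** One column has two current definitions in SAP v1.2, and they cannot both be followed. Under the Appendix 1 row, the Placebo->4mg BD switchers enter both the 4mg BD and the 4mg QD totals, while the Placebo->4mg QD switchers enter no active total.

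The misplaced patients never took 4mg QD. From the tablet table in SAP 13.1, their extension regimen delivers 8 mg a day, against 4 mg a day for the column they would join. SAP 3.1 says the trial's data are needed "so that one or two doses can be selected to progress into further clinical development", and the whole-study safety columns are part of that evidence. Sparse events suffer most in the pooled counts: a post-switch event in a Placebo->4mg BD patient would appear under two doses, and one in a Placebo->4mg QD patient under neither.

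**Working it through.** The plan states no figure for the size of these pools, so there is none to reproduce. The check has two parts.

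**1. Definitions side by side**

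| Column | Switchers added in SAP 16.1.1 | Switchers added in SAP Appendix 1 |
|---|---|---|
| 8mg QD total | Placebo->8mg QD | Placebo->8mg QD |
| 4mg BD total | Placebo->4mg BD | Placebo->4mg BD |
| 4mg QD total | Placebo->4mg QD | Placebo->4mg BD |

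Five of the six cells follow one rule; the last does not. The Appendix 1 row is complete, so a broken table does not explain it. The first table in the same appendix section lists Placebo->4mg QD as a group of its own, yet no total row takes it in. The SAP modification history records no deliberate change to the pooling. A copy from the row above is the likeliest cause.

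**2. Size if outputs follow Appendix 1**

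Inputs from Protocol 1.3: 152 randomized 1:1:1:1; placebo patients pre-assigned 1:1:1 to the three active regimens; two phases of 8 weeks; optional extension. Protocol 9.2.1 gives the 8% dropout allowance.

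- Per arm: 152/4 = 38.
- Per switch sequence with full entry: 38/3 = 12.67.
- Let e be the proportion entering the extension. Switchers per sequence: s = 12.67 × e.
- Headcount share of wrong members: s/(38 + s).
- On-treatment person-weeks: own arm 38 × (8 + 8e); switchers 8s. Share = 8s/[38 × (8 + 8e) + 8s].

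| e | s | Column N | Headcount share | Person-weeks, switchers/total | Person-week share |
|---|---|---|---|---|---|
| 0.92 | 11.65 | 49.65 | 23.5% | 93/677 | 13.8% |
| 0.80 | 10.13 | 48.13 | 21.1% | 81/628 | 12.9% |
| 0.50 | 6.33 | 44.33 | 14.3% | 51/507 | 10.0% |

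The 92% row assumes that all the planned dropout falls before Week 8 and that every completer continues; 80% and 50% are illustrative. Own-arm dropouts are credited with a full 8 weeks, which slightly understates the person-week share.

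One misplaced patient with an event shifts the column by 1/49.65 = 2.0% to 1/44.33 = 2.3%.

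With 1:1:1 switching, the expected column size is the same under either definition, so a check on N alone might not reveal the error.

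**Daily amounts** (SAP 13.1, Table 1): 4mg BD is 2 × 2 mg in the morning plus 2 × 2 mg in the afternoon, 8 mg; 4mg QD is 2 × 2 mg in the morning plus 0, 4 mg.

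**The case against.** The best answer is that this is a typing slip in a display appendix. SAP 16.1.1 is the analysis section, it is unambiguous, and it defines the pooled terms before later sections use them. The faulty row contradicts its own label, so a careful programmer would probably notice. SAP section 8 says "The templates provided with this SAP describe the presentations for this study", and those templates, which are not available here, may already be right. Rare and serious events are also listed patient by patient, so none would vanish from the report. The affected columns are descriptive: SAP 16 plans no statistical comparison of safety data by default, and the placebo-controlled 8-week tables are not touched. Person-weeks, at 10.0% to 13.8%, describe the misplaced exposure better than headcount does.

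Much of this stands as a limit on the consequence. The harm is conditional, the listings are a safeguard, and the person-week figures belong beside the headcount ones. The death summary in SAP 16.2 uses the same group names but falls outside the stated scope of the Appendix 1 table, so it is affected only if it is built from the same groups.

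None of it removes the contradiction. The row sits in the programming conventions and is expressly applied to the TEAE and ECG tables, so coding from it would be following the plan. Comparing event counts with the overall column could expose the slip, but the SAP does not call for that. It need not, since such checks usually sit in program validation.

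**Conclusion.** The point holds. The Appendix 1 row for the 4mg QD total is inconsistent with SAP 16.1.1 and with the SAP's own pooling rule, and it should be corrected.

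If it were programmed as written, 14.3% to 23.5% of the column's patients, carrying 10.0% to 13.8% of its on-treatment exposure, would be on a different regimen, and a similar number of 4mg QD switchers would be missing from every active total. These figures rest on planned allocation, equal switching and assumed extension entry of 50% to 92%. They are what follows if the appendix is used, not evidence that it was.

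The tables exposed are the whole-study TEAE summaries (SAP 16.1.1 to 16.1.5), the whole-study maximum QTcF summary (16.4.1), and possibly the death summary (16.2).

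**What to change.** In SAP Appendix 1, change the switch group in the 4mg QD total row from Placebo->4mg BD to Placebo->4mg QD, so that it agrees with 16.1.1. Check the output templates and the program that derives the pooled groups for the same slip. In validation, confirm that every placebo patient who enters the extension falls in exactly one active total.

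This costs a one-row SAP correction and a short template and program check. It needs no new data or analyses and changes no dosing.
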